11.3 Session Procedures

Once a participant is identified as eligible, a visit date and time will be scheduled.

Participants will complete all experimental conditions, and are to abstain from vaping for a minimum of 30 minutes prior to the study session.

Roswell Park Protocol No.: I-3234822

The order of completion of Sessions 2-5 and 6-7 will be determined using Latin Square and A/B designs, respectively. Order of ad lib and directed bouts within a session will be determined by A/B designs.

Each laboratory session is expected to take approximately 90 minutes.

Directed vs. ad lib bouts. In the directed bout, participants are instructed to take a 4 second puff on the device every 60 seconds until a total of 8 puffs is reached. In the ad lib bout, participants are free to puff as they like for a defined 15 minute period.

Priming / Habituation Puff: At the beginning of each session, participants will take 1 priming puff and 1 habituation puff at a setting of 10 watts. If 10 watts is too harsh for the participant, wattage may be reduced by 2 until comfort level is obtained. Final wattage will be recorded and used throughout the session.

Session 1: Vaping topography using own-brand liquid

In this condition, we will use an A/B design to compare directed vs ad lib vaping of the participant's preferred product. After each bout, participants will complete a battery of sensory outcome measures. All questionnaires will be administered by the experimenter. Vape assembly and puffing regimen will also be directed by the experimenter. The device used will be a SmokTech® NORD2 or equivalent device. This session will be approximately 90 minutes long.

Sessions 2-5: Relationship of tobacco flavor formulation to vaping topography and sensory evaluation.

In this condition, we will use a 4 (flavor) x 2 (ad lib vs directed) within-subjects design. All liquids will have a 60/40 carrier concentration and 5% nicotine. Three commercial tobacco flavor variants versus one unflavored liquid (EC Blend) will be tested.

Over 4 laboratory sessions (sequence determined by Latin square), participants will complete ad lib and directed bouts (sequence determined by A/B design) using each flavor. After each vape, participants will complete a battery of sensory outcome measures. All questionnaires will be administered by the experimenter.

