19.2 Randomization

Subjects will complete up to 7 sessions. At each session, subjects will complete directed and ad lib bouts of vaping. The order of directed and ad lib bouts will be randomized within participant using a permutation block design (block sizes of 2 and 4).

Session 1 will use their own-brand liquid. No randomization is required.

Sessions 2-5 will evaluate the relationship of tobacco flavor formulation (no flavor and 3 commercial flavor variants) on outcomes. The order of nicotine forms (i.e., what flavor is experienced at a given session) will be randomized using a permuted Latin Square design.

Sessions 6-7 will evaluate the relationship of nicotine formulation (2 forms) on outcomes. The order of nicotine forms will be randomized using a permuted Latin Square design.

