19.4 Primary Analysis

The primary objective is to evaluate the influence of:

Roswell Park Protocol No.: I-3234822

- a. tobacco flavoring composition on vaping topography
- b. synthetic vs. tobacco derived nicotine on vaping topography

The primary endpoints are measures of vaping topography, which are treated as quantitative outcomes and will be summarized by condition (flavor or nicotine composition) and bout (directed or ad-lib) using the appropriate descriptive statistics.

Using data from sessions 1-5, each endpoint will be modeled as a function of flavoring (own, none, and 3 commercial flavors), bout (directed or ad-lib), their two-way interaction, and random subject and site effects using a linear mixed model. Tests about the appropriate contrasts of model estimates will be used to compare:

- i) mean differences between flavors within a type of bout,
- ii) mean differences between bouts within a flavor,
- iii) effects of bout (ad lib – directed) between flavors,
- iv) effect of flavor between bouts.

Using data from sessions 6 & 7, each endpoint will be modeled as a function of nicotine composition (synthetic vs. tobacco derived), bout (directed or ad-lib), their two-way interaction, and random subject and site effects using a linear mixed model. Tests about the appropriate contrasts of model estimates will be used to compare:

- i) mean differences between composition within a type of bout,
- ii) mean differences between bouts within a composition,
- iii) effects of bout (ad lib – directed) between compositions,
- iv) effect of composition between bouts.

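### The primary flavor model makes own brand a fifth flavor level, but own brand is always Session 1 and never randomised, so own-versus-study-liquid differences within a bout type cannot be separated from a Session 1 effect

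*Combined protocol and SAP*

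**What the plan says.** Section 19.4 defines the primary flavor analysis: "Using data from sessions 1-5, each endpoint will be modeled as a function of flavoring (own, none, and 3 commercial flavors". The other terms are bout, the flavor-by-bout interaction, and random subject and site effects. There is no session, period or order term. The first listed comparison is "mean differences between flavors within a type of bout".

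The design sections treat own brand differently.

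- Section 19.2: "Session 1 will use their own-brand liquid. No randomization is required". It then says: "Sessions 2-5 will evaluate the relationship of tobacco flavor formulation (no flavor and 3 commercial flavor variants) on outcomes". The order of those four liquids is set by a permuted Latin square.
- Section 11.3, Session 1: "we will use an A/B design to compare directed vs ad lib vaping", using the participant's preferred product.
- Section 11.3, Sessions 2-5: "we will use a 4 (flavor) x 2 (ad lib vs directed) within-subjects design". For these sessions, "All liquids will have a 60/40 carrier concentration and 5% nicotine". No such statement is made for the own-brand liquid.

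Section 19.5 carries the same models to the sensory measures.

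**The concern.** Own brand is used only in Session 1, and Session 1 uses only own brand. Any difference between own brand and a study liquid within a bout type is therefore also a difference between the first visit and later visits.

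The documents give concrete reasons why Session 1 could differ. Table 1 (Section 11.4) and Appendix E place the PTC, PROP and sodium benzoate tasting in the first session only, shortly before the first bout. Table 1 also lists the optional oral rinse, at the Roswell Park site only, for Visit 1 alone. Session 1 is also the first of the study's laboratory sessions.

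The liquids may differ too. Section 3.1 requires daily use of a nicotine vaping product, and the Appendix B2 screener accepts any flavor category. Own brand may therefore differ from the study liquids in flavor type, nicotine strength and carrier. This part varies by participant, and some own brands may match.

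At stake is the standing of these comparisons. As written, own-versus-study-liquid differences can be reported under the tobacco flavoring objective with the same weight as comparisons protected by the Latin square.

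**Working it through.** **1. The plan's own figure.** Section 19.1 gives 80% power (two-sided paired t-test, alpha 0.05) at 0.47 SD for n = 38 and 0.39 SD for n = 53. The noncentral t distribution gives 80.5% and 79.6%, so both reproduce. This point does not change the sample size.

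**2. Pairs affected.** Five levels give 5×4/2 = 10 pairs per bout type. Own brand is in 4. The four randomised liquids give 4×3/2 = 6.

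**3. Aliasing.** Take 72 completers, Sessions 1-5, two bouts per session, own brand in Session 1 and a balanced 4×4 Latin square in Sessions 2-5. With subject effects, the planned model has 72 + 4 (flavor) + 1 (bout) + 4 (interaction) = 81 columns.

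| Session term | Columns | Rank | Own minus unflavored within a bout | Commercial minus unflavored |
|---|---|---|---|---|
| None (as planned) | 81 | 81 | estimable, but absorbs any Session 1 effect | estimable |
| Linear | 82 | 82 | estimable by extrapolation | estimable |
| Categorical | 85 | 84 | not estimable | estimable |

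**4. What a linear term does.** Write m for the mean session effect over Sessions 2-5 and b for the least-squares slope over those sessions. Session 1 lies 2.5 sessions before their midpoint (3.5 − 1). With session effect s₁ in Session 1, the bias of own minus unflavored is s₁ − m without the term and s₁ − (m − 2.5b) with it. The shifts below, in SD units, are assumed.

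- *First visit only*, s₁ = 0.30: m = 0 and b = 0, so the bias is 0.30 either way.
- *Halving each session* (0.30, 0.15, 0.075, 0.0375, 0.01875): m = 0.28125/4 = 0.070, so the bias without the term is 0.230. The slope is b = −0.215625/5 = −0.0431. The extrapolated Session 1 value is 0.070 + 0.108 = 0.178, so the bias with the term is 0.122.
- *Truly linear*, with Session 1 0.30 above the mean of Sessions 2-5: 0.30 without the term, 0 with it.

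Commercial minus unflavored has zero bias in all three cases.

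Precision also falls. The variance factor is 2/72 = 0.02778 without the term. With it, the factor is 0.02778 + 2.5²/(72×2×5) = 0.03646. The ratio is 1.3125, so the standard error rises by about 15%.

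**5. Illustrative rejection rates.** Mean pairs over Sessions 2-5, from the Section 19.1 attrition table, are (65+58+52+47)/4 = 55.5 at 10% attrition and (68+65+62+59)/4 = 63.5 at 5%. The table below assumes no true liquid difference and an assumed Session 1 shift in SDs of the paired difference. It gives the rejection rate of a nominal 5% paired t-test.

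| Assumed shift | n = 55 | n = 63 |
|---|---|---|
| 0.1 SD | 11.3% | 12.2% |
| 0.2 SD | 30.8% | 34.6% |
| 0.3 SD | 58.9% | 65.0% |

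**6. Contrasts involving bout.** Both bouts occur in every session, so an additive Session 1 effect cancels from the own-brand ad lib minus directed difference and from the own-brand flavor-by-bout contrasts. An effect that differs by bout does not cancel. Own brand is observed only in Session 1, so a Session 1-by-bout effect of 0.3 would enter the own-brand bout contrast in full, and hence its comparison with any study liquid.

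**The case against.** The strongest reply is that nobody intends own-versus-study-liquid as a primary flavor test. The objective concerns tobacco flavoring composition, and own brand may be fruit, candy or menthol. Sections 11.3 and 19.2 describe the flavor evaluation as four liquids in Sessions 2-5. Session 1 has its own stated purpose, comparing the two bouts. Section 19.4 refers to appropriate contrasts and never spells out own brand minus a study liquid. This is a plausible reading, and a reader should not infer that the plan commits to claiming these differences as flavor effects. But Section 19.4 names own brand as a level of the factor, and nothing excludes it from the flavor comparisons or gives them a different status.

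Second, own brand is a sensible reference, and the questionnaires use it as one. Strength, carrier and familiarity are part of what a usual product is. This stands: those differences mislead only if the contrast is read as flavoring alone.

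Third, the plan limits first-visit effects. Section 11.3 states: "At the beginning of each session, participants will take 1 priming puff and 1 habituation puff at a setting of 10 watts". Device type, pre-session abstinence and puffing instructions are the same across sessions, and some participants are recruited by continuing from another study (Section 5). These features may reduce a Session 1 effect but cannot show that it is absent, and the Session 1 tasting remains.

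Fourth, harm is not demonstrated. That is correct. The rejection rates follow from chosen shifts and assume that a preferred product and a study liquid do not truly differ, which the plan gives no reason to expect.

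**Conclusion.** The point holds as one of identification. Within each bout type, 4 of the 10 flavor pairs are completely aliased with any Session 1 effect, and no session term cleanly separates them. They are also usual-product comparisons and not tests of tobacco flavoring composition. This follows from the session layout and does not depend on an assumed effect size.

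Three stronger conclusions are not supported.

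- *The primary flavor analysis is invalid.* The 6 pairs per bout type among the randomised liquids are unaffected and the main tobacco-flavor question remains answerable. The nicotine model uses Sessions 6 and 7 only and is not touched.
- *The own-brand comparisons are biased, with false-positive rates of 11% to 65%.* The documents give neither size nor direction for a Session 1 effect. Those figures are illustrations.
- *The own-brand directed-versus-ad-lib contrast is safe without condition.* It and the own-brand flavor-by-bout contrasts are free of an additive Session 1 effect, but not of one that differs by bout.

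The point should be fixed before analysis: its reach is limited, but it concerns a listed primary comparison and costs little to correct.

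**What to change.** Add one sentence to Section 19.4, for example:

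> Primary flavor contrasts are limited to the four randomised liquids (unflavored and three commercial flavors); own-versus-study-liquid comparisons are non-randomised reference comparisons reported outside the primary inference.

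Keep the own-brand directed-versus-ad-lib contrast, reported as a Session 1 result. Apply the same rule to the sensory models in Section 19.5.

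The sentence can be applied within the five-level fit, where Session 1 data still inform the subject effects, or with a fit to Sessions 2-5 only; refitting is optional. Adding a session term is not a substitute.

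Data collection and sample size do not change. The downside is that own-brand pairs leave the primary inference, so flavor pairs per bout type fall from 10 to 6.

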19.1 Sample Size Determination

The planned sample size is n=72 evaluable patient, who are expected to complete 7 potential sessions, for a total of 504 observations.

However, we anticipate an attrition rate of 5-10% per session and the table below provides expected sample sizes under differing rates of attrition:

Session		1	2	3	4	5	6	7
Subjects Completed	5% Attrition	72	68	65	62	59	56	53
	10% Attrition	72	65	58	52	47	43	38
	5% 1-3 and 10% in 4-7	72	68	65	58	53	47	43

A conservative sample size calculation is based on comparing any two flavors or nicotine formulations using a two-sided paired t-test. The minimum expected sample size per combination is expected to be between 38 and 53; which provides 80% power (at $\alpha=0.05$) to detect a difference of at least 0.47 and 0.39 standard deviations. Since the actual models used in the analysis will account for additional sources of variability and will borrow information across sessions, the actual detectable effect sizes may be larger.

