Appendix E Full Study Timeline

-15 min	PROP, PTC, Sodium Benzoate (1 st session only) Saliva, Urine, Oral Samples (optional)
-10 min	Pre: Questionnaires
0 min	Begin bout 1
15 min	End bout 1 / Collect Product
20 min	Post: Saliva
20 min	Post: Questionnaires
45 min	Begin bout 2
60 min	End bout 2 / Collect Product
65 min	Post: Saliva
65 min	Post: Questionnaires

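### The 19.4 models have no bout-position term although bout order is randomised within participant, so any first-versus-second-bout effect costs precision in the liquid contrasts

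*Combined protocol and SAP*

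**What the plan says.** Every session contains one directed and one ad lib bout of the same liquid. Section 19.2 states: "The order of directed and ad lib bouts will be randomized within participant using a permutation block design (block sizes of 2 and 4". Section 11.3 describes the same step more loosely: "Order of ad lib and directed bouts within a session will be determined by A/B designs".

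Appendix E lists "End bout 1 / Collect Product" at 15 min and the start of bout 2 at 45 min.

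Section 19.4 fits one model to Sessions 1-5 (own liquid, unflavored, three commercial flavors) and one to Sessions 6-7 (synthetic, tobacco-derived). Besides liquid, each contains "bout (directed or ad-lib), their two-way interaction, and random subject and site effects using a linear mixed model". The first contrast listed for the flavor model is "mean differences between flavors within a type of bout", and the nicotine model has the matching one. Section 19.5 reuses these models for the sensory measures. Neither section has a term for bout position, bout order or carryover. Section 19.1 says the models will account for further sources of variability but names none. The only covariates mentioned elsewhere (section 11.4) are affect and food taste preferences, for sensory ratings.

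**The concern.** A bout in second position follows an earlier bout of the same liquid in the same session. Ad lib puffing, liking and relief of urge could plausibly differ between the two positions. If a participant has the ad lib bout first with one liquid and second with another, the within-participant difference between the liquids also contains that position difference. The plan randomises and knows this factor but leaves it in the residual.

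At stake is precision in the within-bout liquid contrasts, which address the primary objectives, and in the secondary contrasts that reuse the models. With 38 to 53 participants expected at Session 7, the plan has little power to spare.

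**Working it through.** **Inputs from the documents.** Gap between bouts: 45 - 15 = 30 min (Appendix E). It is nominal because a directed bout of 8 puffs at 60 s spacing reaches its last puff about 7 min in. Bout order: within participant, blocks of 2 and 4 (19.2). Test: two-sided paired t-test, alpha 0.05, 80% power, n = 38 to 53, detectable difference 0.47 and 0.39 SD (19.1).

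**Assumptions.** Order is redrawn each session. Blocks run from Session 1, with sizes 2 and 4 equally likely. The second bout is shifted by δ, in units of the SD of the paired difference without order noise. The documents give no value for δ, so 0.25, 0.5 and 1.0 are used.

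**Step 1: the plan's own figures.** The noncentral t with n - 1 degrees of freedom gives 0.467 SD at n = 38 and 0.392 SD at n = 53. Both agree with 19.1. The counts also agree: 72 × 0.90^6 = 38.3 and 72 × 0.95^6 = 52.9.

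**Step 2: how often order differs between two liquids.** Blocks have even length, so they can start only at odd sessions. The chances of a start are 1 at Session 1, 1/2 at Session 3, 1/2 × 1/2 + 1/2 × 1 = 3/4 at Session 5, and 1/2 × 3/4 + 1/2 × 1/2 = 5/8 at Session 7.
- If a block starts at Session 7, orders at Sessions 6 and 7 are independent and differ with probability 1/2.
- Otherwise both sessions lie in one block of 4 and differ with probability 2/3.
- P(differ) = 5/8 × 1/2 + 3/8 × 2/3 = 9/16 = 0.5625. Simulation gave 0.564.

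The same reasoning for pairs within Sessions 2-5 gives 0.50 to 0.75, mean 7/12 = 0.58.

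**Step 3: added variance.** In a within-bout liquid difference, position contributes +δ, -δ or 0. The signs are balanced by randomisation, so the mean is 0 and the added variance is 0.5625 δ². The SD is multiplied by √(1 + 0.5625 δ²).

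**Step 4: size for the Session 6-7 contrast.** Power uses the normal approximation Φ(2.802/multiplier - 1.960). For δ = 0.5 this is Φ(2.802/1.068 - 1.960) = Φ(0.664) = 75%.

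| δ | SD multiplier | Detectable, n = 38 | Detectable, n = 53 | 80% power becomes |
|---|---|---|---|---|
| 0 | 1.000 | 0.467 | 0.392 | 80% |
| 0.25 | 1.017 | 0.475 | 0.399 | 79% |
| 0.5 | 1.068 | 0.498 | 0.419 | 75% |
| 1.0 | 1.250 | 0.583 | 0.490 | 61% |

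**Step 5: simulation with and without adjustment.** The Session 6-7 paired difference within one bout type was analysed alone and with the order difference as covariate, 6,000 runs per setting.

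| δ | n = 38, effect 0.47: unadjusted / adjusted power | n = 53, effect 0.39: unadjusted / adjusted power |
|---|---|---|
| 0 | 81.4% / 80.1% | 79.6% / 78.8% |
| 0.25 | 79.6% / 79.9% | 78.1% / 78.4% |
| 0.5 | 75.5% / 79.5% | 74.2% / 78.6% |
| 1.0 | 62.7% / 80.7% | 60.6% / 79.0% |

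Bias was at most 0.006 SD and type I error 0.045 to 0.057, with or without the term. When there is no position effect, adjusting costs about one point of power.

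**The case against.** **No bias.** A reader might infer that carryover confounds the liquid comparisons. It does not: order is randomised, and the simulation shows bias near zero and type I error near 5% without any order term. This stands in full. Averaging the ad lib minus directed contrasts over randomised order is also a legitimate marginal estimand.

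**Not every contrast.** In the directed bout participants are told to "take a 4 second puff on the device every 60 seconds until a total of 8 puffs is reached". Puff count and spacing are therefore set by instruction and have little room to move. This stands. Per-puff volume, peak flow, the ad lib measures and the post-bout ratings remain open to a position effect.

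**The first bout is not nicotine-free either.** Participants "are to abstain from vaping for a minimum of 30 minutes prior to the study session", the same length as the nominal gap between bouts. A reader might infer that second bouts are known to be heavily nicotine-loaded relative to first bouts. The documents give no elimination rate and no figure for the extra load. A second bout does follow one more laboratory exposure, so the positions differ, but by an unknown amount.

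**The power loss is assumed.** Section 19.1 does not say which SD it uses. If it is the SD observed under this design, order noise is already in it, and adjustment would be a gain over 80% rather than protection of 80%. Also, n = 38 to 53 are Session 7 counts. The plan's table gives 47 to 59 at Session 5, so the detectable differences above describe the nicotine contrast and not the flavor contrasts.

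**Order may be fixed per participant.** Section 11.3 could be read that way, and an additive shift would then cancel. Blocks of 2 and 4 within a participant make sense only if order varies across sessions, so 19.2 favours the other reading. The sections should still be aligned.

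**Conclusion.** The point holds as one of precision. Bout order is randomised within participant and the second bout follows soon after the first, yet neither 19.4 model (nor 19.5 by reference) adjusts for position. On the natural reading of 19.2, order differs between Sessions 6 and 7 in about 56% of participants and between pairs of Sessions 2-5 in 50-75%, so a position effect does not cancel within participants. It adds noise and leaves chance imbalance uncorrected, chiefly in ad lib topography and post-bout sensory and liking outcomes.

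The loss is trivial at a shift of 0.25 SD, about 5 points of power at 0.5 SD and about 19 at 1.0 SD. These figures rest on the assumed shift, equally likely block sizes, order redrawn each session, and an SD that excludes order noise. The documents do not support a claim of systematic bias, of harm to every within-bout contrast, or of a demonstrated nicotine carryover.

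**What to change.** In 19.4, and so in 19.5, add bout position within session (first or second) as a fixed effect, together with position-by-bout type, to both models. Report the liquid contrasts adjusted for position. State that the ad lib minus directed contrasts are averaged over the two positions with equal weight, since the interaction makes them depend on that choice.

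Align 11.3 with 19.2 by stating whether bout order is redrawn at each session.

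Any ad lib minus directed comparison restricted to first-position bouts should be labelled descriptive. Each liquid is used in one session, so a participant supplies only one first-position bout per liquid and the comparison becomes largely between participants. With an even split of 38 (19 against 19), an unpaired t-test detects only about 0.93 SD of the outcome at 80% power.

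The cost is a sentence or two and two extra fixed-effect parameters per model, with no added visits, samples or participants and no change to conduct. The added terms would not remove a carryover that differs by liquid.

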Vape assembly and puffing regimen will also be directed by the experimenter. The device used will be a SmokTech® NORD2 or equivalent device. These sessions will be approximately 90 minutes long.

Sessions 6-7: Relationship of nicotine formulation to vaping topography and sensory evaluation.

In this condition, we will use a 2 (nicotine form) x 2 (ad lib vs directed) within-subjects design. All liquids will have a 60/40 carrier concentration and 5% nicotine. The primary comparison is between 5% synthetic nicotine and 5% tobacco-derived nicotine.

Over 2 laboratory sessions (sequence determined by A/B design), participants will complete ad lib and directed bouts (sequence determined by A/B design) using each liquid form. After each vape, participants will complete a battery of sensory outcome measures. All questionnaires will be administered by the experimenter.

Vape assembly and puffing regimen will also be directed by the experimenter. The device used will be a SmokTech® NORD2 or equivalent device. These sessions will be approximately 90 minutes long.

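### The primary models have no session-level random effect although both bouts of a liquid share one session, so any session variance makes the liquid-by-bout interaction standard errors too large

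*Combined protocol and SAP*

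**What the plan says.** Section 19.4 sets out two linear mixed models. One uses sessions 1-5 and five liquids (own brand, unflavored, three commercial tobacco flavors). The other uses sessions 6-7 and two nicotine forms. In each, the endpoint depends on liquid, bout, "their two-way interaction, and random subject and site effects using a linear mixed model". Four kinds of contrast follow:

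- (i) liquids compared within a bout type, for nicotine "mean differences between composition within a type of bout";
- (ii) bouts compared within a liquid;
- (iii) for nicotine, "effects of bout (ad lib – directed) between compositions";
- (iv) the liquid effect compared between bouts.

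Section 19.5 applies the same models to the sensory measures.

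On the design, section 19.2 states "At each session, subjects will complete directed and ad lib bouts of vaping". It randomizes the order of liquids over sessions, that is, "what flavor is experienced at a given session". For the nicotine part, section 11.3 says "Over 2 laboratory sessions (sequence determined by A/B design), participants will complete ad lib and directed bouts", with one session per form. Wattage starts at 10 watts, may be lowered, and is then fixed: "Final wattage will be recorded and used throughout the session". Section 19.1 remarks in general terms that the final models will allow for further variance sources, but neither it nor any other section names a session or subject-by-liquid term.

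**The concern.** Liquid is assigned to sessions and bout type varies inside a session, which is a split plot. The two bouts of one session share the day, the liquid, the device set-up, the wattage and the participant's state that day. They can be expected to resemble each other more than two bouts on different days with different liquids. A model with only subject and site effects treats both pairs as equally alike and pools all within-subject variation into one residual.

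Contrasts that live inside a session, chiefly the interaction, are then judged against an error that wrongly contains between-session variation. Contrasts (iii) and (iv) ask whether a liquid effect seen under directed puffing differs under free puffing. A null answer could simply reflect the wrong error term.

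**Working it through.** **The plan's own figure.** Section 19.1 states "The planned sample size is n=72 evaluable patient" and 5-10% attrition per session. Expected completers at session 7 are 72 × 0.95^6 = 52.9 and 72 × 0.90^6 = 38.3. For a two-sided paired t-test at 5% with 80% power, the exact noncentral t gives 0.392 SD at n = 53 and 0.467 SD at n = 38. The plan's 0.39 and 0.47 reproduce.

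**Notation.** Let u be the session (subject-by-liquid) variance, b the subject-by-bout variance, e the remaining error (taken as equal in both bouts), and K the number of liquids. The session share is r = u/(u+e). The documents give none of these, so r = 0.3, 0.5 and 0.7 are assumptions, scaled so that u + e = 1. Data are taken as complete. A site effect is constant within a participant who attends one site and cancels from every contrast below.

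**Pooled residual.** The within-subject mean squares have these expectations: subject × liquid (K−1 df) e + 2u; subject × bout (1 df) e + Kb; subject × liquid × bout (K−1 df) e. The planned model averages them over 2K−1 df:

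R = e + [2(K−1)u + Kb]/(2K−1)

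- Sessions 6-7 (K = 2): R = e + 2(u+b)/3.
- Sessions 1-5 (K = 5): R = e + (8u+5b)/9.

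**Planned against true variance (times n).**

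- (i) liquid within a bout: 2R against 2(u+e).
- (ii) bout within a liquid: 2R against 2(b+e).
- (iii), (iv) interaction: 4R against 4e.

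The ratio of planned to true standard error (SE) is the square root of each quotient. For a test with 80% power under the right error, power becomes Φ(2.80 − 1.96 × ratio). The type I error of a nominal 5% test is 2Φ(−1.96 × ratio).

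**Results with b = 0.**

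| | r = 0.3 | r = 0.5 | r = 0.7 |
|---|---|---|---|
| Sessions 6-7: R | 0.900 | 0.833 | 0.767 |
| Interaction SE ratio | 1.134 | 1.291 | 1.599 |
| Interaction power | 72% | 61% | 37% |
| Nicotine within-bout SE ratio | 0.949 | 0.913 | 0.876 |
| Its type I error | 6.3% | 7.4% | 8.6% |
| Sessions 1-5: R | 0.967 | 0.944 | 0.922 |
| Interaction SE ratio | 1.175 | 1.374 | 1.753 |
| Interaction power | 69% | 54% | 26% |
| Flavor within-bout SE ratio | 0.983 | 0.972 | 0.960 |
| Its type I error | 5.4% | 5.7% | 6.0% |

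With b = 0 the bout contrasts (ii) have the same SE ratios as the interaction. A simulation of 20,000 two-session trials (n = 38, r = 0.5) gave type I errors of 7.7% for nicotine within bout, 1.3% for bout and 1.2% for the interaction. Paired analyses against the correct error gave 4.6-5.2%. Forty REML fits at r = 0.5, comparing the planned model with one that adds a subject-by-session effect, gave SE ratios of 0.913 for nicotine within bout and 1.296 for bout and interaction.

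**Results with b above zero (sessions 6-7, u = e = 0.5).**

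| b | 0 | 0.25 | 0.5 | 1 |
|---|---|---|---|---|
| R | 0.833 | 1.000 | 1.167 | 1.500 |
| Interaction SE ratio | 1.29 | 1.41 | 1.53 | 1.73 |
| Nicotine within-bout SE ratio | 0.91 | 1.00 | 1.08 | 1.22 |
| Bout within nicotine form SE ratio | 1.29 | 1.15 | 1.08 | 1.00 |

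The interaction ratio only grows with b. The other two can change direction. The nicotine SE is too small only if 2(u+b)/3 < u, that is b < u/2. The bout SE is too large only if 2(u+b)/3 > b, that is b < 2u.

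**The case against.** The size of u is unknown and could be small. At r = 0.1 with b = 0, the interaction SE ratio in sessions 6-7 is 1.04 and the nicotine within-bout test runs at 5.4%; at r = 0 there is no error at all. This stands as a limit on size. Wattage set anew each session and individual preferences among liquids make exactly zero implausible. It also stands that the one robust effect is conservative: it costs power and does not create false positives.

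Four stronger readings are tempting, and the documents do not support them.

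- *A reader might infer that the nicotine comparison is anti-conservative.* That requires b < u/2. The directed bout prescribes puff number and spacing while the ad lib bout is free, so participants may well differ in their bout effect. With b = u/2 the SE is right, and above that it is too large.
- *A reader might cite liquid effects averaged over bouts*, whose true variance times n is 2u + e. With b = 0 their type I error in sessions 6-7 would be about 10, 14 and 19%. Section 19.4 does not list that contrast.
- *A reader might infer that the sample size is undermined.* Section 19.1 rests on a paired difference, whose variance 2(u+e) already contains the session component.
- *A reader might think a random session intercept alone is enough.* At r = 0.5 and b = 0.5 in sessions 6-7, it estimates the session variance as u − b/2 and the residual as e + b. The nicotine within-bout SE is then too large by √(1.25/1) = 1.12, and the interaction SE by √(1.0/0.5) = 1.41. It is also not equivalent to an unstructured 2×2 covariance, because it forces equal bout variances and a non-negative covariance.

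**Conclusion.** The gap is real: the stated random effects do not match the randomization structure, and no other section supplies the missing term. The robust consequence is that SEs for the interaction contrasts (iii) and (iv) are too large in both models whenever session variance exceeds zero. The factors of 1.13-1.60 (nicotine) and 1.18-1.75 (flavor) rest on an assumed r of 0.3-0.7, no subject-by-bout variance and equal error variance in the two bouts. Any subject-by-bout variance makes them larger.

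SEs for contrasts (i) and (ii) are generally wrong, without a fixed direction. The 6-9% type I error for nicotine within bout is the case of no subject-by-bout variance. Under that same condition, flavor within bout barely changes.

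The factors apply mainly to per-puff volume, peak flow rate and total volume. Puff count, and largely inter-puff interval, are set by protocol in the directed bout, so equal bout variances are not credible there. This is a defect of the analysis model that should be corrected before analysis; it is not a defect of the design or of the sample size.

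**What to change.** In section 19.4, and by reference in 19.5, specify random subject, subject-by-session (the same as subject-by-liquid, since each liquid has one session within a model) and subject-by-bout effects, with bout-specific residual variance. An equivalent structured covariance would also serve, for example an unstructured 2×2 covariance across bouts at the participant level and another at the session level. State Kenward-Roger or Satterthwaite degrees of freedom.

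Both added effects are needed. Subject-by-bout alone leaves a residual of e + u once b is at least u/K, so the interaction SE stays too large by √((u+e)/e) = 1.20, 1.41 and 1.83 at r = 0.3, 0.5 and 0.7.

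For puff count and inter-puff interval the bout-specific variance is essential. If the directed value is constant, its covariance with the ad lib value is zero, so a session intercept is estimated as zero and repairs nothing. For these endpoints use the form with separate bout variances at both levels. If the directed value does not vary at all, analyze the ad lib bout alone.

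The cost is SAP wording and model code, with no extra data or participants. The model is slightly more complex, and some contrasts may become a little wider. If session variance turns out near zero, almost nothing is lost.
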